### **Clinician, Administrator, Office Professional and Staff confidentiality**

For enrolled clinicians, administrators, office professional, and staff all data collection will be completed by trained research staff and all data will be kept in secure locations at either Centerstone Research Institute or at Indiana University. Data, both quantitative (questionnaires) and qualitative (focus group transcripts, consultation transcripts, and individual interview transcripts) will be associated with an anonymous 6-digit research identification number for each participant. Data completed via the online survey will be stored in secure databases on password-protected computers at Indiana University. Any hard copies of data (should clinicians, administrators, staff, and/or office professionals complete surveys in person) will be transferred to an electronic database; hard copies will be kept in locked cabinets in locked rooms and destroyed at the end of the funding period.

### **Client confidentiality**

All client data collection throughout the study will be conducted by trained research personnel, will only be labeled with anonymous 9-digit research identification numbers, and will be kept in locked cabinets at both the Centerstone and Indiana University research sites and stored in secure, password protected databases on password protected computers accessible only to study research personnel.

### *Ensuring security and feasibility of automated telephone surveys.*

Automated telephone surveys will be employed to assess MBC fidelity (using a yes/no/did not attend session option regarding clinician discussion of the PHQ-9 measure with the client) throughout the study. The automated telephone survey will be set to text or call the enrolled study clients in advance of each scheduled psychotherapy session with the enrolled clinician based on a code triggered by the Electronic Health Record.. Frequency of use of mobile technologies is increasing for assessment and intervention, with data suggesting that underserved and disadvantaged populations are typically owners of mobile phones making this a feasible data collection method (Foley et al., 2012). Additionally, automated telephone surveys serve as a secure and confidential way for clients to respond to the MBC fidelity questions as the client can respond with their touch-tone keypad, thus ensuring that question content and responses remain private and confidential. It is unlikely that enrolled Centerstone clients will not own a telephone; however, in these rare cases (determined during the initial screening/consenting process) the Centerstone research assistants will schedule to meet the client on-site for hard copy administration of the PHQ-9.

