## C6. MBC Fidelity

In this proposal, fidelity to MBC is a three-level categorical variable defined by (a) client completion of the PHQ-9 (No=0, Yes=1), (b) clinician review of scores in the electronic health record (No=0, Yes=1), and (c) discussion of scores in session (No=0, Yes=1). The former two (PHQ-9 completion and clinician review of scores) will be automatically captured through the electronic health record. Clinicians will also check a box in the electronic health record progress note to indicate if they discussed scores in session, as this practice optimizes the effectiveness of MBC (Eisen, Dickey, & Sederer, 2000). Given the known limitations to clinician self-report, this latter fidelity criterion will also be assessed with client self-report via an automated telephone survey immediately after their session. In their first month of implementation, all clinicians (regardless of condition) will be asked to indicate factors they perceived to have limited MBC use. Through a drop-down menu embedded in the electronic health record progress note, clinicians will select contextual factors based on the literature (Dowrick et al., 2009; Garland, Kruse, & Aarons, 2003; Valenstein et al., 2009) and clinician-identified factors (from our pilot data); See Appendix for complete list of options (e.g. lack of time, client refused, clinician forgot).

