
**Phase 3: Post Hoc Characterization of MBC Fidelity, Data Analysis, and Manuscript Preparation.** Consistent with the Dynamic Sustainability Framework (Chambers, Glasgow, & Stange, 2013), the approach to MBC implementation has the potential to be adapted by sites in the tailored condition. That is, early in the active implementation process (within the first month), the implementation team will generate a guideline for MBC implementation that is specific to their site. Characterizing fidelity for this condition will need to reflect the guideline established for

ACTIVITIES	Table 4. Study Activities			
	YEAR 1	YEAR 2	YEAR 3	YEAR 4
Study Phase	Phase 1	Phase 2		Phase 3
EHR Modifications				
Clinician Enrollment				
Randomization				
Clinician Assessment				
Active Implementation	Co1	Co2	Co3	Co4
Sustainment Monitoring		10-months for each cohort		
Client Enrollment & Assessment				
Rapid Ethnography				
Qualitative Coding				
Data Analyses				
Characterize MBC Fidelity				
Manuscript Preparation				

Note. Co = Cohort (2-4 sites with 1-2 randomized to each condition).

each site. For instance, if a site set a guideline to administer the PHQ-9 monthly for each client then actual administration will need to be confirmed monthly. Data capture from the electronic health record will also include whether or not the clinician reviewed the PHQ-9 scores prior to or in session. Finally, with respect to coding of MBC review in session the clinician self-report (via the electronic health record) and client report (via automated phone survey) will be triangulated. Concurrently, focus group data will be formally coded (see *C13b. Qualitative and Mixed Methods Data Analysis*) for manuscript preparation.

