## **Phase 2 (Months 8-38)**

*Client's Treatment (weeks 0-11).* Clients in the standardized condition will be asked to complete the hard copy PHQ-9 forms in the waiting room prior to every session with their enrolled study clinician, while clients in the tailored condition will complete the PHQ-9 according to the measurement-based care guidelines defined by the implementation team at each site. In all cases, clients will fill out the hard copy PHQ-9 prior to a session located in waiting room kiosks and completing the survey should only take about five to ten minutes. The client will then hand the completed PHQ-9 to his or her clinicians who will then enter it into the electronic health record so that the clinicians can review the PHQ-9 scores with the clients during the session. The CRI RA will pull the PHQ-9 data for all enrolled clients across the course of their treatment and provide it to the research team using the 9-digit anonymous identification number. In addition to the PHQ-9, clients will be asked to respond to a telephone or text message-based survey after each psychotherapy session to inquire as to whether their clinician discussed PHQ-9 scores in the session immediately preceding (Yes/No/NA) (Appendix C.4). Client can earn \$2 for every survey they complete for up to \$20. So clients may be able to earn an additional \$20 for completing these surveys after each session and the amount attained will be mailed with the \$10 incentive for completing the week 12 PHQ-9 (described below).

*Client's Treatment (week 12).* Clients will be reassessed for depression symptom severity via a phone interview (like the initial screen) at week 12 of their treatment, regardless of number of treatment sessions attended (Appendix C.2). A postcard reminder may be sent to clients before the phone interview as a reminder. The project coordinator and CRI RAs will track client time since entering treatment, beginning with the intake assessment. Clients will be mailed \$20 as an incentive for completing the week 12 assessment.

*Client's Treatment (week 13 and beyond).* Upon completion of the telephone assessment at week 12, PHQ-9 data collection for all enrolled clients will continue to occur according to the site guidelines for the duration of the study funding-period.

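### Section IX sends the client survey on PHQ-9 discussion before each session while four other places send it after; the timing, and the session each answer belongs to, need to be settled

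*Combined protocol and SAP*

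**What the plan says.** Discussion of scores in session is one of the three components of MBC fidelity, the clinician-level co-primary outcome. C6 has clinicians tick a box in the progress note. Because self-report has known limits, it also wants this criterion "assessed with client self-report via an automated telephone survey immediately after their session". C11, Phase 3, says that the clinician's own report and "client report (via automated phone survey) will be triangulated".

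Section VII, Clients, Phase 2 (weeks 0–11) gives the procedure: "clients will be asked to respond to a telephone or text message-based survey after each psychotherapy session", with the question being "whether their clinician discussed PHQ-9 scores in the session immediately preceding". The two client payment paragraphs of Section XI (arrangements and justification) also describe this survey as completed after each session.

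Section IX, under the heading on security and feasibility of automated telephone surveys, says otherwise. There the survey is "set to text or call the enrolled study clients in advance of each scheduled psychotherapy session", on a code from the EHR. The same paragraph describes it as "using a yes/no/did not attend session option regarding clinician discussion of the PHQ-9 measure with the client". Section VII lists the answers as yes, no or not applicable.

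C13a, Aim 1, models whether the PHQ-9 was discussed, encounter by encounter, among encounters with a recorded PHQ-9. It does not say whether the clinician's or the client's report defines that variable.

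**The concern.** Section IX is the only place that describes the trigger, so it is the text from which the survey would be programmed. A client contacted before a session cannot report on that session and can only describe an earlier one. Nothing in the documents says to which session such an answer would be filed.

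The client report exists to check the clinician's report, session by session. If answers are missing, delayed or attached to the wrong encounter, agreement between the two sources means less. Any use of the client report in the encounter-level discussion variable would carry the error with it.

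**Working it through.** The plan gives no figure on this point to reproduce. The check has four steps.

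**1. The statements side by side**

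| Place | When the survey goes out |
|---|---|
| C6 | immediately after the session |
| Section VII, Clients, Phase 2 | after each session, about the one just held |
| Section XI, Clients, payment arrangements | after each session |
| Section XI, Clients, payment justification | after each session |
| Section IX, automated telephone surveys | before each scheduled session |

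Section IX also disagrees with itself: a client cannot say beforehand that a session was not attended.

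**2. What the literal rule loses, whatever the filing rule**

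Let a client attend n sessions, with one survey before each. The survey before session 1 has no study session behind it. (For a client already in treatment, it would point to a session before enrolment.) The surveys before sessions 2 to n cover sessions 1 to n−1. Session n is covered only if a further session is scheduled. So n−1 of n sessions are certain to be asked about: 11/12 = 92% for n = 12 (an assumption, weekly sessions over the 12-week window), and none for n = 1. Recall also runs over the gap to the next appointment rather than immediately after the session.

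**3. Answers filed to the preceding session**

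This is the referent that Section VII's wording implies. Each answer then sits on the session it describes, and misalignment is 0% under every guideline frequency.

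**4. Answers filed to the upcoming session**

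Assumptions, none of them in the documents: the answer filed to session k describes session k−1; the PHQ-9 is due every m sessions; when due, it is discussed with probability q, independently across sessions.

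- m = 1 is the standardized guideline. m = 2 (every other session) and m = 4 (monthly, if sessions are weekly) are the two examples that C10 gives for tailored sites.
- q is not given, so a range is shown. The values 0.386 and 0.134 are the pilot rates of PHQ-9 use in C9. They measure use, not discussion, and only stretch the range.
- Sessions with a wrong status, as a share of all sessions: 2q(1−q) for m = 1, and 2q/m for m ≥ 2.
- Truly discussed sessions that carry a no: 1−q for m = 1, and 100% for m ≥ 2, because the session before was not a PHQ-9 session.

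| q | m = 1 | m = 2 | m = 4 |
|---|---|---|---|
| 1 | 0% | 100% | 50% |
| 0.9 | 18% | 90% | 45% |
| 0.75 | 37.5% | 75% | 37.5% |
| 0.5 | 50% | 50% | 25% |
| 0.386 | 47.4% | 38.6% | 19.3% |
| 0.134 | 23.2% | 13.4% | 6.7% |

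*Share of all sessions with a wrong status.* A simulation of 400,000 sessions at q = 1, 0.75 and 0.5 agreed to within 0.1 percentage point.

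The ordering is not stable. Every-session sites have the larger error than every-other-session sites when 2q(1−q) > q, that is q < 0.5. They have the larger error than monthly sites when 2q(1−q) > q/2, that is q < 0.75. Monthly sites always have half the error of every-other-session sites. Counted only among truly discussed sessions, every-session sites do better than both, but the two sparser guidelines do not differ.

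**The case against.** Section IX is outnumbered four to one. It sits in a section on protection of participants, not on procedures, and its non-attendance option presupposes that the session time has passed. It is most likely a slip, and no place in the documents shows that surveys were in fact sent beforehand. That stands, and it makes this an internal inconsistency rather than a chosen design. It does not remove the need for correction, because the slip is in the one sentence that specifies the trigger.

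The client report supplements a clinician report that is captured separately, and C13a does not say that the client report enters the modelled variable. That stands too: no effect on a planned analysis has been shown, only on the quality of the check.

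Surveys triggered by sessions later missed might seem to be covered by the non-attendance option or by not applicable. That works for a survey sent after the scheduled time. It does not work for one sent before.

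Finally, C13a is written partly in the past tense and reports that 22.8% of patients missed the 12-week interview, so the data may already be in hand. In that case a changed trigger alters nothing, and the remedy becomes documentation and re-linking.

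**Conclusion.** The contradiction is certain and worth correcting. If Section IX was followed, the losses that need no filing assumption are modest: a first survey without a study session behind it, a last session possibly never asked about, and delayed recall. If answers were also filed to the upcoming session, they are shifted by one.

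A reader might infer that this biases the comparison of conditions, with misreporting greatest at tailored sites that use the PHQ-9 less often. The documents do not support that. It requires filing to the upcoming session, which no text states and which Section VII's wording argues against. It requires tailored sites to choose less than every-session use, for which C10 gives only examples. It requires the client report to define the discussed variable, which C13a leaves open. Even granting the filing rule, the ordering by guideline frequency is not monotone over all sessions and reverses at lower discussion rates. The supported statement is that a one-session shift could differ by condition, with size and direction unknown, and that it is zero if answers are filed to the preceding session.

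**What to change.** Rewrite the Section IX sentence so that the survey is triggered after the scheduled session is marked attended in the EHR, in line with C6, Section VII and Section XI. Use one set of response options in Sections VII and IX. Store the session ID with each response, and state that the answer belongs to that session.

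For any answer that was sent before a session, link it by timestamp to the preceding attended session, and drop it only if no such session can be identified. If collection is over, record when the surveys actually went out and how answers were matched. It would also help for C13a to name the report, or the rule combining the two, that defines discussion.

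The cost is one trigger setting, one stored field and a few sentences. With the survey sent after an attended session and its ID stored, misalignment is 0% at every guideline frequency.

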### **SECTION XI: PAYMENT FOR PARTICIPATION**

A. Will subjects be paid for participation in the study (e.g. monetary, free services, gifts, course credit, including extra credit)?

No. Proceed to next section.

Yes. Complete items 1-3 below.

1. Explain the payment arrangements (e.g. amount and timing of payment and the proposed method of disbursement), including reimbursement of expenses.

#### **Clinicians**

We will compensate clinicians \$25 for participation in the 1.5 hour focus group held at the beginning of the active implementation, end of the active implementation, and end of Phase 2 of the study. Quantitative questionnaires will be completed at baseline, 5-months, and 15-months and clinicians will be provided \$50 for each assessment completed in compensation for the time required to complete study measures. Those clinicians on the implementation team will complete a battery of quantitative questionnaires at 5-months and 15-months and will receive \$15 in compensation per assessment point. At sites affected by technology issues, clinicians will be compensated \$1 for each time they answer questions related to PHQ-9 use with clients (see Appendix B.4). In addition, at the beginning of Phase 2 of the study, clinicians will be asked to participate in one four-hour training session that will introduce either the standardized MBC approach or the tailored MBC procedures. Clinicians will receive Continuing Education Units (i.e., education credit needed for licensure) for attending the training. An additional battery of quantitative measures will be completed post-training and clinicians will be provided \$10 in compensation. Clinicians who participate in the exit interviews at 5 month end of active implementation period will receive \$20.

#### **Clients**

All clients who complete the baseline (i.e., initial phone screen) PHQ-9 assessment, regardless of study eligibility, will be mailed an incentive of \$5 for completing the baseline assessment and another \$5 for returning signed study documents. Clients who complete the week 12 PHQ-9 assessment will be mailed a \$10 incentive for completing it. Client can earn \$2 for every phone-based survey they complete for up to \$20. So clients may be able to earn an additional \$20 for completing these text messages after each session and this amount attained will be mailed with the \$10 incentive for completing the week 12 PHQ-9 (described below). In addition, if a client does not have unlimited text messaging, we will offset the costs for the text message surveys by providing the client with \$5. Clients who participate in the three implementation team meetings will receive \$15 per meeting attended.

#### **Administrators**

All administrators who complete the individual interview will be compensated \$20. Those administrators on the implementation team who complete a battery of quantitative questionnaires at 5-months and 15-months and will receive \$15 in compensation per assessment point. Administrators will receive \$50 compensation for completing the battery at the three time points: baseline, at 5-month follow up, and at 10-month follow up.

#### **Office Professionals**

Those office professionals on the implementation team who complete a battery of quantitative questionnaires at 5-months and 15-months and will receive \$15 in compensation per assessment point. All office professionals will be receive \$20 compensation for completing the abbreviated battery at the three time points: baseline, at 5-month follow up, and at 10-month follow up

#### **Staff**

Staff will receive \$20 compensation for completing the abbreviated battery at the three time points: baseline, at 5-month follow up, and at 10 months after active implementation. When a paper version of the baseline is sent, an additional \$1 incentive will be included.

2. Justify the proposed payment arrangements described in section B. (e.g., how this proposed payment arrangement is not considered to be coercive).

#### **Clinicians**

Centerstone clinicians make an average of \$23.5/hour; therefore, this compensation amount is appropriate for the time and effort required for measure completion and focus group participation. The continuing education credits received for attending the MBC training are meant to directly offset the costs of participating.

#### **Clients**

Clients will receive \$10 for each completed PHQ-9 assessment across two time points (over the phone at intake, and via phone in week 12 of treatment). This payment is meant as an incentive to complete the PHQ-9 assessment. An additional \$20 may be earned by completing the phone based messaging survey after each session, which is meant as incentive to complete the text messaging surveys. No compensation/incentive will be provided for client PHQ-9 completion prior to other sessions in order to maximize external validity (i.e., mimic the “real world” situation in which MBC would otherwise be expected to occur without compensation) and to facilitate sustainment

#### **Administrator**

Administrators will receive \$30 for completing an individual interview, \$15 per assessment completed as part of participating on the implementation teams and \$20 for completing the abbreviated battery. We believe these amounts are appropriate for the time and effort required to participate in the individual interviews and complete the battery of questionnaires.

#### **Office Professionals**

Office professionals will receive \$15 per assessment completed as part of participating on the implementation teams and \$20 per abbreviated battery completed. This payment is believed to be an appropriate amount for the time required to complete the battery of questionnaires.

#### **Staff**

Staff will receive \$20 per abbreviated battery completed. This payment is believed to be an appropriate amount for the time required to complete the battery of questionnaires. Staff will receive \$1 when they receive the paper version of the survey. This payment is believed to be an appropriate additional incentive to complete the paper version of the survey.

3. Explain if there will be any partial payment if the subject withdraws prior to completion of the study (e.g. prorated). Note: This payment may be paid at the end of the subject's participation or at the end of the study.

There will not be partial payment. Clinicians who complete the data collection procedures (i.e., assessments and focus groups) will receive the aforementioned compensation or continuing education credits. Similarly, clients who complete the PHQ-9 assessment at baseline and/or session 12 will receive the \$10 incentive for each assessment completed. Administrators and Office professionals who complete the data collection procedures outlined above will receive the previously mentioned compensation.

### **SECTION XII: INFORMED CONSENT PROCESS**

#### **A. I WILL be obtaining informed consent from all subjects.**

1. **When (in what timeframe) and where (what setting) will consent take place?** Indicate any waiting period between informing the subject and obtaining consent. The timeframe and any waiting should ensure the prospective subjects or their legally authorized representatives are provided sufficient opportunity to consider whether or not to participate in the study.

